7. Time to improvement of vital signs.
8. Time to improvement of respiratory status.
9. Improvement on the ordinal scale.
10. Time to hospital discharge.
11. The time to influenza viral negativity based on qRT-PCR and/or viral culture from nasal MT swabs and, if applicable, based on PCR-based rapid molecular testing from nasal MT swabs.
12. Viral load over time and the rate of decline in viral load during treatment as measured by qRT-PCR and/or viral culture.

13. AUC of viral loads as measured by qRT-PCR and/or viral culture.
14. Resistance testing will be performed on all baseline samples as well as on qRT-PCR-positive post-baseline samples. Genotypic assays (sequencing of full length PB2 and other gene segments if applicable) will be used to determine resistance against JNJ-63623872. Phenotyping may be done at the sponsor's discretion. Resistance testing for neuraminidase inhibitors will also be performed as applicable.

Exploratory Endpoints

1. Length of ICU stay for subjects transferred to the ICU after baseline will be collected.
2. Use of antibiotics and/or corticosteroids during hospitalization.
3. Number of subjects admitted to the ICU.
4. Correlation between the decline in viral load (measured by qRT-PCR and/or viral culture) and changes in clinical symptoms.
5. PK/pharmacodynamic (PD) relationship (efficacy and safety).

An independent data monitoring committee (IDMC) will be established to monitor safety and efficacy data on a regular basis.

An interim analysis may be performed to support regulatory activities.

Pharmacokinetic Analyses

Descriptive statistics will be calculated for plasma concentrations of JNJ-63623872 at each sampling time point and for the derived plasma PK parameters. Statistics include sample size (n), mean, standard deviation (SD), %CV, geometric mean, median, minimum, and maximum.

For each subject treated with JNJ-63623872, JNJ-63623872 plasma concentration-time data will be graphically presented. Similarly, graphs of the mean plasma concentration-time profiles and overlay graphs with combined individual plasma concentration-time profiles will be produced. Pharmacokinetic parameters will be subjected to an exploratory graphical analysis in order to get a general overview.

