10.3. Withdrawal From the Study

A subject will be withdrawn from the study for any of the following reasons:

- Lost to follow-up
- Withdrawal of consent
- Death

If a subject is lost to follow-up, every reasonable effort must be made by the study site personnel to contact the subject and determine the reason for discontinuation/withdrawal. The measures taken to follow up must be documented.

When a subject withdraws before completing the study, the reason for withdrawal is to be documented in the eCRF and in the source document. Study drug assigned to the withdrawn subject may not be assigned to another subject. Subjects who withdraw will not be replaced. If a subject withdraws from the study before the end of the treatment or the follow-up phase, he or she will be offered an optional Safety Follow-up Visit.

A subject who withdraws from the study will have the following options regarding the optional research sample:

- The collected sample will be retained and used in accordance with the subject's original separate ICF for optional research samples.
- The subject may withdraw consent for optional research sample, in which case the sample will be destroyed and no further testing will take place. To initiate the sample destruction process, the investigator must notify the sponsor study site contact of withdrawal of consent for the optional research samples and to request sample destruction. The sponsor study site contact will, in turn, contact the biomarker representative to execute sample destruction. If requested, the investigator will receive written confirmation from the sponsor that the sample has been destroyed.

Withdrawal From the Use of Samples in Future Research

The subject may withdraw consent for use of samples for research (see Section 16.2.5, Long-Term Retention of Samples for Additional Future Research). In such a case, samples will be destroyed after they are no longer needed for the clinical study. Details of the sample retention for research are presented in the main ICF.

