The FLU-PRO and Flu-iiQ™ domain scores will be presented descriptively over time using descriptive statistics. A linear mixed model will be used to analyze composite symptom scores over time, per domain. For the Flu-iiQ™ a daily score will be derived averaging observed scores before the analysis. Baseline subject characteristics will be included (in particular baseline score) in case these provide to be predictive of post-baseline scores. Mean differences between treatment arms will be derived from this model using appropriate contrasts and will be presented including the associated 95% CI. For both measures, an AUC of composite symptom scores over a 7- and 14-day period per domain will be calculated and compared using a mixed model for repeated measurements.

Other PRO endpoints that will be analyzed are:

1. Time to return to usual activity and usual health (Questions 5 and 9 of the additional items for the Flu-PRO).
2. Time to significant reduction in influenza symptom severity.
3. Proportion of patients with a significant reduction (to mild or none for all influenza symptoms) at each assessment.

Other Outcomes

The length of overall hospital stay will be calculated from the date of first study drug intake up to the date of discharge. Subjects still hospitalized at the end of the study will be censored at the last contact. Data will be presented using Kaplan-Meier curves. For a comparison between treatment arms, the time to hospital discharge in days will be analyzed using an accelerated failure time model (if the data provide an acceptable model fit) or alternatively a Cox proportional hazards model (in case the hazards are proportional). Additionally, the time to event data will be analyzed using the Gehan-Wilcoxon method. The time to resumption of normal daily activities will be analyzed in an analogous fashion.

Resistance Analyses

The results of viral sequencing and phenotyping will be evaluated by the sponsor virologist. Additional exploratory characterization of the viral genotype and phenotype may be performed and will be reported accordingly.

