3.1.1. Phase Definitions

Table 5: Construction of phases

Trial phase	Trial sub period ^{*1}	Start date	End date
Screening (phase 1)		The date of signing the informed consent with 00:00 as a timepart	1 minute before the first study medication intake
Treatment (phase 2)		Datetime of first study medication intake	Datetime of last investigational medication intake ^{*5} + 24 hours
	Hospitalization (sub period 1) ^{*2}	In case first intake of study medication occurred at the hospital ^{*4} : Datetime of first study medication intake	The minimum of: 
 The last date of discharge from hospital^{*4} + timepart 23:59 The Datetime of last investigational medication intake^{*5} + 24 hours
	Outpatient (sub period 2) ^{*3}	In case first intake of study medication did not occur at the hospital ^{*4} : Datetime of first study medication intake In case first intake of study medication occurred at the hospital ^{*4} and last discharge from the hospital occurred before the end of the treatment	Datetime of last investigational medication intake ^{*5} + 24 hours

Trial phase	Trial sub period ^{*1}	Start date	End date
		phase: End date hospitalization phase ^{*4} + 1 minute	
Follow-up (phase 3)		End of the treatment phase +1 minute	Trial termination date (date of last contact) or cut-off date for the Interim analysis, whichever comes first with 23:59 as a timepart

^{*1}: A treatment period will be constructed in the derived datasets with the same start and end date as the treatment phase.

^{*2}: The hospitalization phase will not be made for subjects that took the first intake of study medication at home.

^{*3}: The Outpatient phase will not be made for subjects that are still in hospital at the end date of the treatment phase

^{*4}: the start date and end date of hospitalization will be derived from the eCRF Hospitalization page. If the start date is not available, the start date of hospitalization will be the date of first treatment (as being hospitalized is an inclusion criterion in the protocol). If the end date is not available the date will be derived from the subject exposure domain as the last visit that is not 'Outpatient' (in case no outpatient visit available in the exposure domain, the subject is assumed to be hospitalized during the entire treatment phase). Should a subject be discharged and again hospitalized during the treatment phase, the entire period will be regarded in the hospitalization phase.

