4.2.1. Clinical Outcomes

▪ **Incidence of influenza complications**

The incidence of influenza complications from first intake up to Day 28 will be categorized in a hierarchical fashion. The overall category will consist of any complication, consisting of the following subcategories

- bacterial pneumonia (culture confirmed where possible),
- other bacterial superinfections,
- respiratory failure,
- pulmonary disease: asthma, chronic obstructive pulmonary disease [COPD]),
- cardiovascular and cerebrovascular disease (eg, myocardial infarction, congestive heart failure [CHF], arrhythmia, stroke),
- post-baseline ICU admission,
- all-cause mortality

The occurrence (yes/no) of influenza complications from first intake up to Day 28 of each (sub) category will be analyzed using logistic regression with treatment group as covariate. In case influenza complications occur in both age categories, age category will also be added as a covariate and as an interaction with treatment group. If the model will not fit the age category and it's interaction will be removed. Odds ratios and associated 95% CIs will be reported of active vs. control treatment and – if available – of elderly patients vs. patients < 65 years.

▪ **Time to improvement of vital signs**

The time to improvement of vital signs is defined as the time (in hours) from first study treatment until the first assessment (actual date and time) of a successive series of 3 recordings (over 4 scheduled successive analysis time points, 1 missing time point is allowed) where at least 4 of 5 symptoms (temperature, blood oxygen saturation, heart rate, SBP, respiration rate) are recovered, with at least normalization of temperature and blood oxygen saturation. Normalization is defined in Table 6. If subjects satisfy these criteria at entry they will be censored at that time.

Only vital signs assessments assessed during hospitalization and up to Day 14 (during hospitalization) will be taken into account to determine time to improvement of vital signs. Assessments taken after hospital discharge or after day 14, whichever, comes first will not be taken into account. In case, there was more than one hospitalization period, only assessments of the first hospitalization period will be used.

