*On room air to be obtained from “Was oxygen saturation measured on room air?” on Vital Signs pages (SUPPVS.QVAL for SUPPVS.QNAM = ‘VSOXSMRA’)

▪ **Time to improvement of respiratory status**

Time to improvement of respiratory status is defined as the time (in hours) from first study treatment until the first assessment (actual date and time) of a successive series of 3 recordings (over 4 scheduled successive analysis time points, 1 missing time point is allowed) where normalization of blood oxygen saturation and respiration rate occurred (as defined in Table 6). Analysis performed will be analogous to the analysis for the time to improvement of vital signs. Note that the NEW Score at baseline should not be added as covariate in the models.

▪ **Clinical outcome on day 8**

The ordinal scale consists of 6 categories that are exhaustive, mutually exclusive, and ordered (Table 7). For all patients, the category at days 1 to 15 will be established as the worst category on that day. The clinical outcome on day 8 will be further analyzed.

The analysis of the clinical outcome on day 8 will be performed using a proportional odds model, modeling the common odds ratio of the improvement on the ordinal scale of active treatment versus control. Age category (≥ 18 - < 65 years, ≥ 65 - ≤ 85 years) and baseline clinical outcome category will be added to the model. In case the model will not fit, age category and subsequently baseline category will be deleted.

In case of missing data ($>10\%$), multiple imputation under the missing-at-random assumption will be employed as a sensitivity analysis. The Markov chain Monte Carlo (MCMC) method will be used to create a number of multiple imputation datasets with monotone missingness in the clinical outcomes (baseline until day 15). The number of imputation datasets will be the same as the percentage of missing data (White *et al.* 2011). A monotone ordinal logistic regression imputation model will be used to complete the remaining missing clinical outcomes. The models fitted using the multiple imputation datasets will be the same as the final model on the actual data. The results from the models on the multiple imputation datasets will be combined taking into account the between and within variation of the results.

Additionally a Wilcoxon–Mann–Whitney test will be performed to compare the clinical outcome on day 8 between the two treatments.

Table 7: Ordinal scale on Day 8

Outcome
Death

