The time to influenza A viral negativity (see definition in section 4.2.2) measured by viral load and viral titer will be correlated with the following clinical measures (see definitions in sections 4.2.3 and 4.2.6):

1. Time to resolution of symptoms (7 primary symptoms)
2. Time to resolution of symptoms (All symptoms)
3. Time to return to usual activity,
4. Time to return to usual health and
5. Time to significant reduction in influenza symptom severity

Scatter plots with smoother curve will be shown per treatment group for the above mentioned correlations. An additional table will be provided showing the spearman correlation coefficients.

- **Correlation between the viral load, viral titer and severity of clinical symptoms**

The post-baseline log₁₀ values of viral load and post-baseline log₁₀ values of viral titer from day 2 to day 7 will be correlated with the following severity of clinical symptoms (see definitions in sections 4.2.3 and 4.2.6):

1. Flu-iiQTM daily average symptom score post-baseline from day 2 to day 7
2. FLU-PRO total score post-baseline from day 2 to day 7

Scatter plots with smoother curve will be shown per treatment group for the above mentioned correlations. An additional table will be provided showing the spearman correlation coefficients.

- **Correlation between baseline viral load, baseline viral titer and clinical symptoms**

The baseline viral load and baseline viral titer will be correlated with the following clinical measures (see definitions in sections 4.2.3 and 4.2.6):

1. Time to resolution of symptoms (7 primary symptoms)
2. Time to resolution of symptoms (All symptoms)
3. Time to return to usual activity,
4. Time to return to usual health and
5. Time to significant reduction in influenza symptom severity

Scatter plots with smoother curve will be shown per treatment group for the above mentioned correlations. An additional table will be provided showing the spearman correlation coefficients.

4.2.9. *Other Outcomes*

▪ **Time to hospital discharge**

The time to hospital discharge will be calculated from the date of first study drug intake during hospitalization up to the date of discharge. Subjects still hospitalized at the end of the study (end date of hospitalization missing or after trial termination) will be censored at the trial termination date.

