- Action taken towards study treatment (Dose increased, Dose not changed, Dose reduced, Dose interrupted, Drug withdrawn)
- Relation to study treatment (Not related, Doubtful, Possible, Probable, Very likely)
- Outcome of AE
- AE leading to death (Yes/No)
- Concomitant treatment taken (Yes/No)
- Influenza-related complication (Yes/No)
- Anticipated AE (Yes/No)
- Required hospitalization/prolonged hospitalization (Yes/No)

The adverse events will be shown by MedDRA system organ class and preferred term, in order of descending overall frequency.

Summaries of TEAEs will be presented overall and by the severity of the AE and relationship to the study drug.

AEs leading to death, SAEs, AEs leading to dose interruption, and AEs leading to permanent discontinuation will be listed separately. All AEs through the Safety Follow-up Visit will be listed in an individual subject data listing, including pre-treatment AEs. Spontaneous adverse events reported after the Safety Follow-up Visit, including unresolved, ongoing adverse events will be listed as well.

Anticipated Events

An anticipated event is an AE (serious or non-serious) that commonly occurs as a consequence of the underlying disease or condition under investigation (disease related) or background regimen.

For the purposes of this study the following events will be considered anticipated events (see Appendix 1 for the classification of AEs into Anticipated Events and Anticipated Event Groups):

- Bacterial pneumonia
- Bronchitis
- Sinus infections
- Ear infections
- Worsening of asthma, asthma attack
- COPD exacerbation
- Complications of sickle cell disease, sickle cell crisis
- Complications of diabetes mellitus, diabetic ketoacidosis
- Acute respiratory distress syndrome (ARDS)

Frequency tabulations of anticipated events and anticipated event groups will be shown by treatment. The Incidence of Treatment Emergent anticipated events will

be compared between active treatment versus placebo by a one-sided Fisher exact test (significance level < 0.10).

▪ **Influenza-related complications**

Adverse Events reported as influenza-related complications will be tabulated overall and by category and adverse event. A listing showing the AEs reported as influenza-related complications and complication information will be made linking the information to the AE listing.

The categories of influenza related complications as recorded on the eCRF are:

- Bacterial Pneumonia
- Bacterial Superinfections,

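### Time to hospital discharge does not require discharge alive and has no rule for in-hospital death, so the Kaplan-Meier proportion discharged is overstated by up to the in-hospital mortality

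*SAP*

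**What the plan says.** "Time to hospital discharge" is a secondary endpoint in the Protocol Synopsis. SAP 4.2.9 runs the clock from the first in-hospital dose to the discharge date and gives one censoring rule, for subjects still in hospital at study end: "end date of hospitalization missing or after trial termination) will be censored at the trial termination date". Protocol 11.6 has the same idea: "Subjects still hospitalized at the end of the study will be censored at the last contact". Neither passage mentions death or the word alive.

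Two other passages fix what the rule does:
- SAP 3.1.1, Table 5, explains the censoring date: "Trial termination date (date of last contact").
- Protocol 10.3 includes death in the list that begins "A subject will be withdrawn from the study for any of the following reasons".

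SAP 4.2.9 plans Kaplan-Meier curves and estimates, an accelerated failure time (AFT) model as the arm comparison, a Cox model if the AFT fit is unacceptable and hazards are proportional, and logrank and Gehan-Wilcoxon analyses. No competing-risk method is named.

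Death is handled elsewhere. In SAP 4.2.1 it is the worst ordinal category, assigned daily ("For all patients, the category at days 1 to 15 will be established as the worst category on that day"), and "all-cause mortality" is counted to Day 28. SAP 4.3.1 lists "AEs leading to death, SAEs, AEs leading to dose interruption".

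**The concern.** A subject who has died in hospital will never be discharged. Censoring at death tells the Kaplan-Meier estimator that discharge was still possible, with the same prospects as for those who remain. Counting the death date as a discharge treats the worst outcome as the best. Either way the curve shows more people going home than did, even when mortality is equal in the two arms.

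At stake is the reading of the discharge table and curve. In a hospitalized influenza population they could show nearly everyone discharged while some subjects had died. The choice between codings would also be left to programming.

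**Working it through.** **1. Figure to reproduce.** There is none. The documents give no expected stay, discharge proportion or in-hospital mortality for this endpoint, so all such inputs below are assumptions.

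**2. What the rule does with an in-hospital death.**
- End date missing: the rule applies and censors at last contact. Death ends participation, so that is about the date of death.
- Death date entered as end date: it is neither missing nor after termination, so the rule does not apply and the date counts as a discharge.
- Table 5 of SAP 3.1.1 (footnote 4) replaces a missing end date by the last non-outpatient visit in the exposure data. That is written for building study phases. Reused here, it would create a false discharge date.

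**3. Size in general.** Take n subjects, L discharged alive and D dead in hospital by Day 28, with no other censoring before then. The proportion discharged alive is L/n.
- Death as discharge gives (L + D)/n, an excess of exactly D/n.
- Censoring at death passes each dead subject's weight to those still in hospital. The excess is D/n if all of them later go home, and less if some do not or if deaths come late.

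**4. Small example.** Sixty subjects: 57 go home alive by Day 14 and 3 die in hospital (Days 5, 8, 12). Both default codings reach 100%; the proportion discharged alive is 57/60 = 95.0%. With 6 deaths in 60 it is 54/60 = 90.0%, and with 1 in 30 it is 29/30 = 96.7%, again against 100%.

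**5. Constant hazards.** Let m be the median time to discharge without deaths and p the in-hospital mortality by Day 28. Then r = ln 2/m, and d solves d/(r+d) × (1 − exp(−28(r+d))) = p.
- Discharged alive: F = r/(r+d) × (1 − exp(−28(r+d))).
- Kaplan-Meier with deaths censored: K = 1 − exp(−28r).
- Death as discharge: 1 − exp(−28(r+d)), which exceeds F by exactly p.

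For m = 6 and p = 5%: r = 0.1155, d = 0.0063, K = 96.06%, F = 91.70%, excess 4.36 points.

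| m (days) | K | F at p = 2 / 5 / 10% | K − F (points) |
|---|---|---|---|
| 4 | 99.22% | 97.29 / 94.40 / 89.55% | 1.93 / 4.82 / 9.67 |
| 6 | 96.06% | 94.32 / 91.70 / 87.28% | 1.74 / 4.36 / 8.78 |
| 10 | 85.64% | 84.29 / 82.24 / 78.78% | 1.35 / 3.40 / 6.86 |

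**6. Comparison of arms.** Simulation with 60 active and 30 placebo, log-normal stay (log SD 0.7), and deaths of 10% vs 3% placed at random on Days 2 to 10.
- Median stay 5 days in both arms: Day 28 Kaplan-Meier is 99% vs 99% under either default coding and 89% vs 96% with deaths kept (0.90 × 0.993 = 0.894; 0.97 × 0.993 = 0.963).
- The same with deaths on Days 8 to 20: 97% vs 98% censored, 89% vs 96% kept.
- Mortality 5% in both arms: 99% instead of 94%, with a Cox hazard ratio of about 1 under every coding.

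Cox hazard ratios for discharge, active vs placebo, with deaths on Days 2 to 10 (ranges over repeat runs):

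| Median stay, active vs placebo | Censored at death | Death as discharge | Deaths kept |
|---|---|---|---|
| 5 vs 5 days | 0.91–0.94 | 0.99–1.02 | 0.80–0.83 |
| 4 vs 5 days | 1.18–1.23 | 1.28–1.34 | 0.99–1.02 |

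In the first row the default codings shrink or remove a difference; in the second they create one. With 5-day stays in both arms, the AFT ratio is 1.05 censored and 1.05 kept (late deaths 1.07 and 1.05; 40:20 allocation 1.04 and 1.04). Median stays are 5.9 vs 5.6 days censored and 6.0 vs 5.6 kept.

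**The case against.** **The planned comparison hardly moves.** The AFT model is the main comparison and Cox only a fallback, and SAP 4.2.9 does not name a Day 28 proportion. This stands. A reader might infer that the main treatment comparison is invalid; the figures do not support that. What is wrong is mainly the displayed proportion discharged.

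**The eCRF is not available.** This stands too. A reader might infer that the plan definitely counts deaths as discharges, or definitely censors them at death. The documents settle neither. They do show that no written clause keeps a dead subject as not discharged.

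**Censoring at death is a recognised choice.** In a Cox model it gives a cause-specific hazard ratio, a legitimate quantity. It does not make the Kaplan-Meier complement a proportion discharged, and the SAP does not declare that choice.

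**The effect is small and deaths are visible elsewhere.** This is fair: SAP 4.2 rules out formal testing, and mortality appears in the complications, ordinal and adverse event outputs. It limits the severity. The discharge display would still be wrong on its own terms.

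**Conclusion.** The omission is real. On either recording of an in-hospital death, the Kaplan-Meier proportion discharged is too high by roughly the in-hospital mortality by Day 28, and by somewhat less when deaths are censored and come late relative to discharge. In the constant-hazard cases with 5% mortality, the excess is 3.4 to 4.8 points with deaths censored and 5 points with deaths counted as discharges. This holds with equal mortality in the arms.

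A reader might also infer that the gap always dilutes a treatment difference or hides harm. The documents do not support that. The direction depends on mortality, timing of death and length of stay, none of which they give, and the simulations show both directions. The 10% vs 3% mortality is purely illustrative.

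The correction is worth making before unblinding. Its reach is limited to one secondary endpoint with no formal testing, with deaths reported elsewhere.

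**What to change.** Add to SAP 4.2.9:

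> The event is discharge alive. A subject who dies before discharge is never an event and is kept as not discharged, censored at Day 28, in all analyses of this endpoint, including the AFT model. All other subjects are cut at Day 28. An end date equal to the date of death is not a discharge unless a live discharge that day is documented. The 3.1.1 fallback for a missing end date is not used to create a discharge date.

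Then:
- Report the Day 28 proportion discharged alive per arm beside the model result, because the AFT ratio does not show the deaths. If living inpatients are lost before Day 28, use the Aalen-Johansen estimate with death as a competing event.
- State that a Cox model with deaths kept estimates a subdistribution hazard ratio. The cause-specific ratio, with deaths censored, may be added as a labelled supplement.

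The common Day 28 cut gives deaths and living inpatients the same end of follow-up. It does not rest on the ±3-day final-visit window, which belongs to the after-discharge schedule; the inpatient schedule shows no window on Day 28.

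Cost: SAP wording and one derivation line. No new data are needed, since the SAP already identifies deaths by day to Day 15 and counts them to Day 28.
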